7.3.2 Acceptability analysis

In order to assess the acceptability and feasibility of implementation of the newly proposed triaging and treatment algorithms we will adopt a mixed methods study design. Quantitative data will be collected through pre-structured questionnaires, while in-depth interviews will also be conducted to complement and illustrate the quantitative study results. We will recruit participants, and health care workers (HCW's) from each participating sites (5 in Ethiopia, 2 in Nigeria, 2 in South Africa) as well as relevant policy makers from each country. For the collection of quantitative data, per site, we will interview at least 10-25 participants (50 per country), 7-15 HCWs depending on the number of HCW's directly involved in the implementation and execution of the intervention, approximately 35 per country, and at least 3 policy makers (one at national, one at provincial and one at district level (i.e., programmatic management of DR-TB [PMDT] focal persons in each country). For the qualitative data collection, we will continue data collection until data saturation has been reached, although this will not be feasible for the policy makers, as there is only one to be interviewed per level. We will purposively and concurrently sample interviewees to include maximum variability: men and women from different participating sites, participants assigned to different regimens with or without comorbidities, fully or partly adherent to therapy, HCWs and stakeholders with different job description and years of experience in the setting.

We will train local interviewers (one per participating site) on the topic guide, interview competences, and obtaining informed consent. The trained interviewer will conduct interviews using the pre-structured questionnaires and semi-structured in-depth individual interviews. Interviewers will be supervised by a local focal person with background in qualitative research, who will also oversee interview activities, and data collection (including quality and data saturation) and storage. All communication during interviews will be in the local language. We will obtain a-priori written informed consent for audiotaping the in-depth interviews and publication of anonymized results. Following each in-depth interview, the interviewer will describe interview setting, including ambiance and emotions, and verbatim transcribe and translate audio-recorded interviews in English. Interviewees will receive a small incentive for the time spent on the interview.

Analysis of the quantitative data will be done using statistical software (Stata or SPSS). Proportions and median/mean values will be calculated as appropriate. Differences between subgroups will be analysed. For the qualitative part, after familiarization with the data, two researchers will analyse data (QSR Nvivo10 software) by using an applied thematic approach, which allows for inductive coding and thematising. After development of a coding scheme, which will be refined along the coding process, two researchers and an independent reviewer (one from each participating site) will regularly discuss interpretation of data, coding, and emerging (sub)themes. Additional to overarching study results, we will stratify analysis per country, health care worker/participant perspective, gender, and type of regimen received. We

will present study results by themes, including relevant interviewee quotes. This exercise will be conducted after each interview to judge if new themes arise from the interview. If no new themes arose, data saturation was reached and no more in-depth interviews will be conducted for that specific group of participants. We define acceptability as a multi-faceted construct that reflects the extent to which people delivering or receiving a healthcare intervention consider it to be appropriate, based on anticipated or experienced cognitive and emotional responses to the intervention. Both persons receiving (participants) and delivering (health care workers (HCW) and policy makers) the intervention will be included in the assessment. Feasibility reflects how viable implementation of the intervention is. Both the (anticipated and experienced) acceptability and feasibility will affect the intervention's uptake and effectiveness.

8. TREATMENT CONSIDERATIONS

8.1. Interruptions to treatment

The study treatment regimen may be interrupted at the discretion of the local PI for:

- A serious adverse event
- The investigator decides to withhold treatment in the interest of the safety and well-being of the participant
- Lack of effectiveness

If treatment is interrupted for a suspected serious drug reaction, attempts should be made to identify the drug concerned. After resolution of the suspected adverse reaction, treatment may be gradually re-introduced until the allocated regimen has been re-instituted.

In the case of the BPaL regimen, if treatment is interrupted for more than 35 consecutive days, the participant will be referred to the assigned expert TB clinical committee to decide on further management including need for change to a new individual regimen, based on clinical assessment and reason for interruption. Any missed doses should be made up at the end of the treatment to complete 24 weeks of therapy. Missed doses of linezolid alone due to adverse reactions are not to be made up at the end of treatment. Reasons for missing treatment must be identified and addressed early and noted in the participant's file for analysis for factors associated with (lack of) treatment success (33).

In the event that the local PI considers that treatment needs to be modified or changed, he or she should inform the coordinating centre by submission of an SAE form and discuss treatment plans with a member of the study medical monitoring team (MMT).

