8.2. Discontinuation of treatment due to toxicity or treatment failure

The study regimens will be discontinued in some participants. In such cases, participants will be evaluated by the MMT and switched to an individualized regimen, based on the WHO guidelines for regimen design. The most common situations in which the regimen may be discontinued include:

- **Intolerable severe toxicity.** One or more drugs may need to be suspended permanently due to severe toxicity. In such cases, the clinical committee should review the medical history carefully to determine how the regimen should be modified (see discontinuation/modification criterion below).
- **Treatment failure.** If clinical and bacteriological responses to treatment are poor, a change in the treatment regimen should be considered. DST should be repeated if culture is still positive at month 4, whether or not the regimen is changed, in order to inform future management decisions.
- **Resistance to drugs in the regimen.** For participants who submit a sputum sample for culture-based second-line DST at the beginning of treatment, results may not be available until after treatment has started. If resistance to component drugs is discovered after treatment is initiated, it may be necessary to modify, extend treatment duration or discontinue the regimen.
- **Pregnancy during treatment.** For participants who become pregnant during treatment, it may be advisable to modify or discontinue novel regimens. A decision regarding continuation or discontinuation of the regimen should be made after a review by the study MMT and discussion with the participant

For participants discontinued from study treatment or whose treatment is changed and participants referred to the NTP, every effort should be made to continue passive follow up (at a reduced frequency if necessary), unless the participant has specifically withdrawn consent for further follow-up. In this event, a final status form should be completed. Details for management these participants will be outlined in a study specific SOP.

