The estimated XDR prevalence among MDR cases is 4.3% in South Africa (2018 Global TB report), 0.6% and 0.7% in Nigeria and Ethiopia (2019 Global TB report). This would mean that N=880*4.3% = 38 XDR cases. As BPaL eligibility extends to pre-XDR patients and treatment intolerant MDR patients, it is expected that a higher number will be on BPaL. A total of 40 participants (including 15% LFU) are needed to detect an improvement from 53% to 85%. This number should be possible for all sites together. Assuming approx. 10% HR-TB in each site, we aim to enrol N=400 in cohort 2 which would allow for approximately 100 HR-TB participants per site, which should be sufficient for studying associated secondary study outcomes.

9.2. Analysis including statistical methods:

Primary endpoint analysis:

- The time to appropriate treatment initiation will be calculated as median days (with interquartile range) between the first sputum collection date and the date of start of the regimen appropriate to the drug resistance pattern (defined as drug-resistance pattern appropriate treatment). This will be compared to the same time in the historical cohort and stratified by geographical location (study site). Confounding will be addressed by multivariable analysis.
- The proportion of favourable study outcomes [treatment cure or completion, based on the WHO definitions (5) will be calculated in the overall study population of cohort 1, and compared with the same proportion in the historical cohort, and stratified by geographical location (study site). In a secondary analysis, these proportions will also be calculated per type of DR-TB. Confounding will be addressed by multivariable analysis.

Both of these outcomes will only be calculated in the primary cohort (cohort 1), as no reliable historical data exist for either endpoint for HR-TB (cohort 2).

Secondary endpoint analysis:

- Prevalence of HR-TB stratified by geographical location. This will be calculated in cohort 2 and stratified by HIV status.
- The incidence of adverse events will be divided into adverse events and serious adverse events and calculated in proportions using both cohort 1 and 2. These will also be stratified by type of DR-TB, treatment regimen, and HIV status.
- Feasibility and acceptability (participant and health care provider perspective), stratified by type of DR-TB regimen (cohort 1 and 2)

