10.3. Serious Adverse Event Reporting

An SAE or Serious Adverse Reaction (SAR) or Suspected Unexpected Serious Adverse Reaction (SUSAR) includes an experience where any AE, AR or UAR that at any dose:

- Results in death;
- Is life-threatening;
- Requires hospitalization or prolongation of existing hospitalization;
- Results in persistent or significant disability or incapacity; or is a medically significant/important event or reaction that may not be immediately life-threatening or result in death or hospitalization but may jeopardize the participant or may require intervention to prevent one of the other outcomes listed in the definition above.

All serious ADRs will be reported.

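### Section 8.1 asks for an SAE form whenever treatment is changed, which does not match the SAE definition in section 10.3 and creates a risk of misclassified SAEs

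*Protocol*

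**What the plan says.** - **Section 8.1 (interruptions to treatment).** The last paragraph applies whenever "the local PI considers that treatment needs to be modified or changed". In that case "he or she should inform the coordinating centre by submission of an SAE form", and the investigator also discusses treatment plans with the medical monitoring team (MMT). The trigger is the change itself; seriousness is not mentioned.
- **Section 10.3 (SAE reporting).** An SAE "includes an experience where any AE, AR or UAR that at any dose" leads to one of the listed outcomes: death, threat to life, hospital admission ("Requires hospitalization or prolongation of existing hospitalization"), lasting disability, or a medically important event that "may jeopardize the participant or may require intervention to prevent one of the other outcomes listed in the definition above". Change of treatment is not listed.
- **Section 8.2 (discontinuation).** If resistance to a component drug is found after treatment has started, "it may be necessary to modify, extend treatment duration or discontinue the regimen". For participants who become pregnant, "it may be advisable to modify or discontinue novel regimens".
- **Section 9.2 (secondary endpoints).** "The incidence of adverse events will be divided into adverse events and serious adverse events and calculated in proportions", in cohorts 1 and 2, stratified by type of DR-TB, regimen and HIV status.
- **Section 13.5 (Good Clinical Practice).** In South Africa, SAEs go to the ethics committee and the regulator within 7 business days of site awareness.

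**The concern.** The SAE form serves two purposes: it records serious harm, and it is the notice that treatment has been changed. A site following 8.1 literally would file an SAE form for a switch made only because of a laboratory resistance result. Nothing in the protocol says what happens to that form afterwards.

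If some of these forms were classed as SAEs, the SAE proportion would partly reflect how often regimens are adjusted. Because 9.2 stratifies by regimen and DR-TB type, and the frequency of adjustment plausibly differs between those strata, any misclassification could also differ between them. A second possible consequence is needless SAE processing at sites and at the coordinating centre. Neither consequence is certain, but the present wording leaves both open.

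**Working it through.** The protocol states no expected SAE or modification rate, so there is no figure to reproduce. The check sets the sections side by side.

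1. **Trigger against definition.** The 8.1 trigger is an action, namely that treatment needs changing. The 10.3 definition needs an adverse event or reaction plus a listed outcome. The first does not imply the second.
2. **Do foreseen changes fall outside 10.3?** Two in section 8.2 can. Resistance found on a late susceptibility result is a laboratory finding and need involve no adverse event. Pregnancy as a reason for review is not in itself one of the listed outcomes. Resistance-driven switches are expected in this study: section 4.4.2 makes the proportion of participants with bedaquiline and linezolid resistance that warrants a switch a secondary objective.
3. **Do some changes fall inside 10.3?** Yes. A change made for toxicity may meet the medically important criterion, so the overlap is not zero. The protocol gives no reason to think that it is complete.
4. **Is there a stated way to tell the forms apart?** Section 10.1 has each AE report record the action taken with the drug and the seriousness of the event as separate items. That helps when an adverse event lies behind the change. When none does, there may be no AE report to carry a seriousness item, and 10.1 gives no rule for an SAE form sent only as notice.
5. **What would the effect on the SAE proportion be?** Let p be the proportion of participants with an event meeting 10.3, and m the share of the remaining participants whose treatment is changed without such an event.
   - If every SAE form were counted: p + (1 − p) × m.
   - If only events meeting 10.3 are counted: p, whatever m is.
   - The difference is (1 − p) × m. The protocol gives neither p nor m, and does not say which counting rule applies. Any percentage would rest on invented inputs.
6. **Population.** Section 9.2 uses both cohorts, planned at 880 + 400 = 1280 participants, so 880 alone is not the denominator. South Africa, where the 7-business-day rule applies, is planned to enrol 440 of the 880 in cohort 1, which is half.

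**The case against.** The strongest case on the other side is that 8.1 uses the form only to inform the coordinating centre. It does not say that a submitted form is an SAE. Section 9.2 reports serious adverse events, 10.3 defines them by outcome, and 10.1 records seriousness separately. An analyst who applies 10.3 gets the right proportion, and the counting rule may stand in an analysis plan that is not at hand. Further, resistance and pregnancy come from 8.2, which has its own route (MMT evaluation and a study procedure) and names no SAE form. Resistance to BPaL component drugs found after enrolment is also a late exclusion criterion in section 6.5.

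Much of this stands, and it rules out three stronger readings:

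- A reader might infer that the reported SAE proportion is inflated. The documents do not support this, since no section says that each SAE form is counted as an SAE.
- A reader might infer that regulators and the DSMB will receive these forms. Section 8.1 sends them to the coordinating centre; the reporting duty in 13.5 covers SAEs, and nothing says that every form is passed on.
- A reader might count poor response among the changes that involve no adverse event. Section 10.1 includes lack of efficacy in its definition of an adverse drug reaction, so that example fails.

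The objection does not remove the conflict. The 8.1 sentence covers any modification or change, in words not limited to interruptions, and 8.2 does not exempt its own cases. The safeguard in 10.1 is for AE reports. An analysis plan could define the numerator, but it cannot stop sites filing forms that the protocol tells them to file.

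**Conclusion.** Sections 8.1 and 10.3 are inconsistent. The protocol states a site instruction that calls for SAE forms in situations that its own definition does not class as SAEs. The result is a risk of misclassification in the SAE proportions of 9.2, and of needless entry into the SAE reporting of 13.5. It is not a demonstrated bias.

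The size cannot be derived from the protocol. It would be nil if every form is judged against 10.3 before counting, and otherwise would depend on how often treatment is changed without a qualifying event. The conclusion rests on reading the 8.1 sentence as written, so that it reaches the changes described in 8.2. Neither primary outcome is affected. The point takes no position on when treatment should be changed.

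**What to change.** Reconcile 8.1 with 10.3:

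- In 8.1, replace the SAE form with a short treatment-modification notice to the coordinating centre and the MMT, with a field for the reason for the change.
- In the same sentence, require an SAE form only when the underlying event meets 10.3.
- In 9.2, state that only events meeting 10.3 enter the SAE proportion.

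The cost is one new form and a sentence or two of text. If SAE forms have already been filed under the present wording, each should be checked once against 10.3 before the safety analysis. No dose, regimen or stopping rule changes.

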8.2. Discontinuation of treatment due to toxicity or treatment failure

The study regimens will be discontinued in some participants. In such cases, participants will be evaluated by the MMT and switched to an individualized regimen, based on the WHO guidelines for regimen design. The most common situations in which the regimen may be discontinued include:

- **Intolerable severe toxicity.** One or more drugs may need to be suspended permanently due to severe toxicity. In such cases, the clinical committee should review the medical history carefully to determine how the regimen should be modified (see discontinuation/modification criterion below).
- **Treatment failure.** If clinical and bacteriological responses to treatment are poor, a change in the treatment regimen should be considered. DST should be repeated if culture is still positive at month 4, whether or not the regimen is changed, in order to inform future management decisions.
- **Resistance to drugs in the regimen.** For participants who submit a sputum sample for culture-based second-line DST at the beginning of treatment, results may not be available until after treatment has started. If resistance to component drugs is discovered after treatment is initiated, it may be necessary to modify, extend treatment duration or discontinue the regimen.
- **Pregnancy during treatment.** For participants who become pregnant during treatment, it may be advisable to modify or discontinue novel regimens. A decision regarding continuation or discontinuation of the regimen should be made after a review by the study MMT and discussion with the participant

For participants discontinued from study treatment or whose treatment is changed and participants referred to the NTP, every effort should be made to continue passive follow up (at a reduced frequency if necessary), unless the participant has specifically withdrawn consent for further follow-up. In this event, a final status form should be completed. Details for management these participants will be outlined in a study specific SOP.

8.3. Interruptions to care

8.3.1. Missed Visits

For each participant, clinic staff will obtain or confirm contact information. In the event that a participant misses a scheduled appointment, staff will try within the week following the missed appointment to establish telephonic communication with the participant and/or treatment supervisor through all possible means which they have approved while protecting their confidentiality. Permission for this contact must be obtained in the initial consent form. All attempts to locate a participant following each missed appointment will be documented in the source document. The need to attend all scheduled follow-up visits will be emphasized to all study participants at every visit. Every site will develop its own method for tracing and retaining participants in the study.

Participants who miss their scheduled appointment will be contacted and arrangements made for a new appointment. If participants are not successfully reached by phone/text messaging, a home visit will be arranged to ensure contact. Participants returning after missed appointments will have procedures for the visit closest to their total time in follow up performed. Subsequent visits will continue as scheduled. However, treatment to be prescribed should be determined by the actual number of days already taken and not by time in the study.

A participant will be deemed to be missing if he/she does not attend the treatment centre to take the treatment as prescribed for a period of one week. If the participant has not resumed

treatment within seven days, i.e., the participant has missed at least two weeks of treatment; a note should be made in their clinic notes with details of attempts to contact the participant.

8.3.2. Loss to follow-up

Every effort will be made to keep participants engaged in follow-up. If the participant does not return to the clinic before the study is closed, the final form will be completed at the time of study closeout. The form should indicate that the participant was lost to follow-up. The “loss to follow-up” designation cannot be made for any participant until at least 3 months after the participant’s scheduled visit.

9. STATISTICAL CONSIDERATIONS

9.1. Power and Sample size calculations:

The study will be powered based on the two primary endpoints:

- i) Numbers needed to detect a reduced time to resistance-pattern appropriate treatment initiation for all drug-resistant cases compared to the historical cohort; and
- ii) The difference in proportion of favourable treatment outcomes compared to the historical cohort, allowing for stratification by study site (geographical location).

Current data, mainly from South Africa, show a median time to resistance-pattern appropriate treatment initiation for drug-resistant participants between 15 and 46 days (1-3). With an assumption of an anticipated time to treatment initiation of one week in our study (allowing time for providing repeat sputum samples and delays in Xpert testing), 220 RR-TB participants must be enrolled in cohort one in each country (440 in South Africa), to achieve 90% power to show a shortening of time to treatment initiation. This sample size includes an allowance for an overall 15% loss to follow-up.

Table 6: Reported median times (in days [IQR]) to treatment of drug-resistant TB in literature

Patient type	Xpert-based	LPA-based	Phenotypic DST-based	Location/date	Ref	
All	MDR+XDR	17 [9-47]	38 [23-54]	81 (49-115)	Johannesburg, South Africa 2017	(34)
	RR	0 [0-1]	20 [10-16]	106 [30-124]	Multi-site 2011 (Boehme)	
	MDR	8 [5-25]	50		MSF Cape Town 2015	(35)
	MDR	17 [13-22]	43 [40-46]		Cape Town 2014	(36)
	MDR	15 [1-29]	32 [7-57]		South Africa 2017	(37)

	RR (only 4 pts)	2	21	40 (MGIT)	Cape Town South Africa 2011	
	MDR			88 [29-126]	Korea 2019	(38)
	XDR			97 [79-126]	Korea 2019	(38)
Smear positive	MDR + XDR	15 [1-42]	32 [7-42]	81 [75-107]	Johannesburg, South Africa 2017	
Smear negative	MDR + XDR	-	54 [45-62]	Johannesburg, South Africa	Johannesburg, South Africa 2017	

For the proportion of favourable study outcomes, we used the most recent treatment completion proportions of Kwazulu-Natal province of South Africa, including one of the study sites (4). The average MDR-TB treatment completion proportion is 63%, varying from 57% in their long regimen to 74% using a bedaquiline-based short regimen. The study sample size of n=220 per study site as calculated above will be sufficient to detect an improvement in treatment outcomes with a minimum difference from 74% to 85% (80% power; larger differences with 90% power [from baseline success of 71% and less]), also allowing for 15% loss to follow-up.

The estimated XDR prevalence among MDR cases is 4.3% in South Africa (2018 Global TB report), 0.6% and 0.7% in Nigeria and Ethiopia (2019 Global TB report). This would mean that N=880*4.3% = 38 XDR cases. As BPaL eligibility extends to pre-XDR patients and treatment intolerant MDR patients, it is expected that a higher number will be on BPaL. A total of 40 participants (including 15% LFU) are needed to detect an improvement from 53% to 85%. This number should be possible for all sites together. Assuming approx. 10% HR-TB in each site, we aim to enrol N=400 in cohort 2 which would allow for approximately 100 HR-TB participants per site, which should be sufficient for studying associated secondary study outcomes.

9.2. Analysis including statistical methods:

Primary endpoint analysis:

- The time to appropriate treatment initiation will be calculated as median days (with interquartile range) between the first sputum collection date and the date of start of the regimen appropriate to the drug resistance pattern (defined as drug-resistance pattern appropriate treatment). This will be compared to the same time in the historical cohort and stratified by geographical location (study site). Confounding will be addressed by multivariable analysis.
- The proportion of favourable study outcomes [treatment cure or completion, based on the WHO definitions (5) will be calculated in the overall study population of cohort 1, and compared with the same proportion in the historical cohort, and stratified by geographical location (study site). In a secondary analysis, these proportions will also be calculated per type of DR-TB. Confounding will be addressed by multivariable analysis.

Both of these outcomes will only be calculated in the primary cohort (cohort 1), as no reliable historical data exist for either endpoint for HR-TB (cohort 2).

Secondary endpoint analysis:

- Prevalence of HR-TB stratified by geographical location. This will be calculated in cohort 2 and stratified by HIV status.
- The incidence of adverse events will be divided into adverse events and serious adverse events and calculated in proportions using both cohort 1 and 2. These will also be stratified by type of DR-TB, treatment regimen, and HIV status.
- Feasibility and acceptability (participant and health care provider perspective), stratified by type of DR-TB regimen (cohort 1 and 2)
- Cost-effectiveness (cost per person tested and incremental cost per DR-TB participant timely initiated on the resistance pattern-appropriate regimen) and, following from that, optimal placement of Xpert XDR in diagnostic & treatment algorithm (cohort 1 and 2)
- Accuracy of Xpert XDR testing (in comparison with culture + DST/LPA/Next-generation sequencing [NGS]), by type of DR-TB (cohort 1 and 2)
- Operational feasibility of Xpert XDR testing (infrastructure requirements and HR needs) (cohort 1 and 2)
- Quality of Xpert XDR tests (indeterminate rate, DNA contamination rate, and performance variation [in time and between sites]) (cohort 1 and 2)
- Clinical utility and feasibility of TB-MBLA in bacteriological follow-up of DR-TB (in comparison with routine culture), by type of DR-TB and regimen (cohort 1)
- Additional resistance to new and repurposed drugs, by type of DR-TB and regimen (cohort 1 and 2)
- Mathematical modelling of TB-MBLA trajectories in response to treatment

Timing of analysis:

The majority of the above outcomes will be analysed after the end of follow-up, however an interim analysis of the primary study outcomes as well as the safety outcomes is planned for Month 32 (M32) or after complete Month 12 follow-up (M12FU). This will allow for timely informing of policy makers as these new diagnostic tools and regimens are being rolled out.

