Study Duration	48 months: study enrolment will occur over 12 -18 months
Sample Size	A total of 1280 participants will be enrolled between 2 prospective study cohorts: Cohort 1 (newly diagnosed DR; rifampicin resistance [RR-TB] participants; n=880) and Cohort 2 (rifampicin sensitive and isoniazid, fluroquinolone and or second line injectable drug (SLID) resistant participants; HR-TB; n=400). Data from a historical cohort (Cohort 3; n=220) of RR-TB participants that accessed DR-TB care at each implementing site over the last 2 years (approximately 24 months) prior to study start.

Study sites	South Africa (n=2), Nigeria (n=6) and Ethiopia (n=5)
Study population	Adult participants (18 years and over) who test positive for pulmonary M.tb with HR-TB or RR-TB will be approached for study participation
Study intervention	Xpert MTB/XDR assay as a triage test to guide early initiation of an appropriate all-oral DR-TB treatment regimen

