6.2. Selection of Participants

Approximately 4800 participants will be screened across the 13 sites (in South Africa, Nigeria and Ethiopia) to enrol 1280 eligible participants. All presumptive TB patients presenting for diagnosis at the study sites will be approached for screening. Each of the sites will also contribute to the historical cohort as described below.

6.2.1. Selection of cohort 1

880 RR-TB (n=440 in SA, n=220 in Nigeria and n=220 in Ethiopia) participants will be enrolled into Cohort 1. Each participant in cohort 1 will be followed up for the duration of TB treatment and passively thereafter to a maximum of 18 months from TB treatment initiation.

6.2.2. Selection of cohort 2

400 HR participants into Cohort 2 (n=200 in SA, n=100 in Nigeria and Ethiopia). Each participant in cohort 2 will be followed up passively for the duration of TB treatment and passively thereafter to a maximum of six months.

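### The per-site outcome power (80% for 74% v 85%, 90% from 71%) needs about 187 to 220 historical patients in each stratum; Table 1 most naturally gives 220 in all

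*Protocol*

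**What the plan says.** Section 9.1 opens with "The study will be powered based on the two primary endpoints". It describes the second endpoint as "The difference in proportion of favourable treatment outcomes compared to the historical cohort, allowing for stratification by study site (geographical location". The size claim for that endpoint is "The study sample size of n=220 per study site as calculated above will be sufficient to detect an improvement in treatment outcomes". Two figures go with this claim: 80% power when success rises from 74% to 85%, and 90% power when baseline success is 71% or lower. Attrition of 15% is said to be covered. Section 9.1 gives no historical sample size, allocation ratio, alpha or sidedness.

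Section 6.2.1 sets the prospective side: "880 RR-TB (n=440 in SA, n=220 in Nigeria and n=220 in Ethiopia) participants will be enrolled into Cohort 1". Section 6.2 adds that every site contributes to the historical cohort, with no split by country or site.

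The only figure for the historical cohort is in Table 1 (section 1): "Data from a historical cohort (Cohort 3; n=220) of RR-TB participants that accessed DR-TB care at each implementing site". The same row gives cohort 1 as n=880 and cohort 2 as n=400, both study totals.

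Section 9.2 calculates the favourable-outcome proportion in cohort 1 overall, "compared with the same proportion in the historical cohort, and stratified by geographical location (study site".

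**The concern.** The power of a two-group comparison depends on both groups, and the smaller one dominates. Section 9.1 justifies 220 patients per location as if that number alone fixed the power. If the whole historical cohort is 220 patients spread over three countries, each country has far fewer comparators than cohort 1 patients, and the per-site 80% and 90% cannot hold.

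At stake is how location results are read. The protocol plans to inform policy makers early (section 9.2, timing of analysis). If Nigeria or Ethiopia shows no clear improvement, a reader told that each location had 80-90% power could take that as evidence of no benefit. With 55 to 73 historical patients in the country, a true rise from 74% to 85% would be missed about half the time.

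**Working it through.** **Inputs.** Proportions 74% v 85% and 71% v 85%, and 15% loss (section 9.1). Cohort 1: 440 / 220 / 220 in South Africa, Nigeria and Ethiopia (section 6.2.1), or 374 / 187 / 187 after multiplying by 0.85. Historical cohort: 220 (Table 1).

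**Assumptions.** Alpha 5% two-sided, because none is stated. If 220 is the total, it splits either equally (about 73 per country) or in proportion to cohort 1 (110 / 55 / 55).

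**Formula.** With h historical and c prospective patients, p̄ = (h·p1 + c·p2)/(h + c), SE0 = √[p̄(1−p̄)(1/h + 1/c)] and SE1 = √[p1(1−p1)/h + p2(1−p2)/c]. Power = Φ[(p2 − p1 − 1.96·SE0)/SE1]. The unpooled variant puts SE1 in place of SE0. The continuity-corrected variant subtracts ½(1/h + 1/c) from the difference.

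**Step 1: reproduce the stated power.**
- 74% v 85%, 220 v 220: p̄ = 0.795, SE0 = 0.03849, SE1 = 0.03813. Power = Φ[(0.11 − 0.07544)/0.03813] = Φ(0.906) = 81.8%.
- 74% v 85%, 220 historical v 187: 78.2%. With 187 v 187: 75.2%. The formula needs 211 per group for 80%, or 249 after dividing by 0.85.
- 71% v 85%, 187 v 187: p̄ = 0.78, SE0 = 0.04284, SE1 = 0.04222. Power = Φ[(0.14 − 0.08397)/0.04222] = Φ(1.327) = 90.8%.
- A one-sample test against a fixed 74% gives 96.4% (n=187) to 98.5% (n=220), so it does not explain the 80%.

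The stated figures therefore correspond to about 187 to 220 historical patients per stratum. The 80% matches best without the 15% loss and the 90% matches with it.

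**Step 2: power for 74% v 85% if the historical cohort is 220 in all.**

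| Stratum | Historical v cohort 1 | Pooled | Unpooled | Continuity-corrected |
|---|---|---|---|---|
| Nigeria or Ethiopia | 55 v 187 | 47.4% | 39.8% | 40.2% |
| Nigeria or Ethiopia | 55 v 220 | 49.1% | 40.6% | 42.0% |
| Nigeria or Ethiopia | 73 v 187 | 54.1% | 48.0% | 47.5% |
| Nigeria or Ethiopia | 73 v 220 | 56.2% | 49.2% | 49.8% |
| South Africa | 73 v 374 | 61.7% | 52.2% | 55.9% |
| South Africa | 110 v 440 | 75.5% | 68.3% | 71.4% |

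Worked example, 55 v 187: p̄ = 0.825, SE0 = 0.05828, SE1 = 0.06465. Power = Φ[(0.11 − 0.11423)/0.06465] = Φ(−0.065) = 47.4%.

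For 71% v 85% in Nigeria or Ethiopia, power runs from 55.7% (55 v 187, unpooled) to 73.8% (73 v 220, pooled), against 90% stated. The most favourable case there (one-sided 5%, pooled, 73 v 220) gives 67.1% for 74% v 85% and 82.2% for 71% v 85%, still below both claims.

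**Step 3: overall comparison, 74% v 85%.** With 220 v 748 (880 × 0.85): SE0 = 0.02914, SE1 = 0.03233. Power = Φ[(0.11 − 0.05711)/0.03233] = Φ(1.636) = 94.9%. With 187 v 748 it is 92.4% (88.8% unpooled).

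**Step 4: historical records needed for 80% at 74% v 85% in a country.** 200 if all 220 of cohort 1 are evaluable, 246 if 187 are.

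**The case against.** The strongest objection is that n=220 may not be a total. Section 9.1 uses site to mean country or location: its 220 per study site points back to 220 in each country, and it equates study site with geographical location. Table 1 attaches n=220 to care at each implementing site. Read as 220 per stratum, the historical group is the size the formula needs, and power is 75-82% for 74% v 85%. This stands as a possible reading. A reader might infer that location-level power falls to about half whatever the protocol meant, and the documents do not support that: the shortfall depends on what the 220 counts. The other cohort sizes in the same row are totals, so 220 in all remains the more natural reading, but the text does not say so.

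A third reading, 220 at each of the 13 facilities, would mean 13 × 220 = 2,860 records, with 5 × 220 = 1,100 from Ethiopia. Section 2.2 reports 658 laboratory-confirmed RR/MDR cases in all of Ethiopia in 2019, so this is implausible.

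A reader might also infer that the outcome endpoint as a whole is underpowered. It is not: section 9.2 first compares cohort 1 overall, where power is about 92-95%. The second primary objective (section 4.3) names no stratification, and the protocol specifies no separate significance test per country for this outcome. Allowing for stratification can mean one stratified estimate. What remains is the explicit per-site power statement.

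Lastly, the 40-56% range should not be extended to South Africa. With 440 enrolled there, two-sided power is about 52-76%. With 110 v 440 the pooled figure for 71% v 85% is 90.2%, which meets the stated 90%.

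**Conclusion.** The concern holds for the per-site power claim only. Section 9.1 states 80% and 90% power at location level, which requires about 187 to 220 historical patients per stratum, and Table 1 does not clearly provide them.

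- **If the historical cohort is 220 in all:** the claim fails in Nigeria and Ethiopia under every variant tried, by roughly 24 to 40 percentage points two-sided for 74% v 85% (80 − 56 and 80 − 40). South Africa also falls short of 80% two-sided, by less.
- **If it is 220 per country:** the claim roughly stands, slightly short at 75.2% once the stated 15% loss is applied to both groups.

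On either reading the two sections need reconciling. The sizes rest on an assumed 5% alpha and an assumed country split of the historical cohort. Confounder adjustment is not included and could change power further. The overall comparison is sound, so this is a should-fix.

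**What to change.** Reconcile Table 1 with section 9.1. State the historical n in total and per stratum, the alpha and the sidedness, and restate power for that allocation. Settle the intended n before writing in any replacement figure, because the country figures above rest on an assumed split.

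- **If the total is 220:** name the overall location-stratified comparison as the powered analysis (about 92-95% for 74% v 85%), withdraw the per-site 80% and 90% claims, and report country results as estimates with confidence intervals.
- **If 220 per country was meant:** say so in Table 1, and correct the 80% for the 15% loss or state that the loss does not apply to the historical records.
- **Optional:** where registers allow, abstract about 200 to 250 historical records per country to keep the location-level claim.

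The first two are changes of wording. If the total is 220, the stated location-level power becomes less favourable. The optional route adds register and chart abstraction but no new participants.
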